### 12.8.2.4. Quality of Life (QoL)

Patient improvement in Quality of Life will be reported. The difference between the Quality of Life scores at 6 months, 12 months, 18 months, and 24 months will be compared to the baseline values. Quality of Life will be measured using the EuroQOL Five Dimensions Questionnaire (EQ-5D-5L)

### 12.8.2.5. Subgroup Analyses

The effectiveness analyses will be evaluated in each of the following subgroups:

- 1) Women
- 2) Men
- 3) Reduced Ejection Fraction (< 40%)
- 4) Preserved Ejection Fraction ( $\geq 40\%$ )
- 5) Ischemic Etiology
- 6) Non-ischemic Etiology
- 7) With ICD/CRT-D
- 8) Without ICD/CRT-D

### 12.8.2.6. Subject Contact

All contact between site staff and study subjects post implant will be documented and the frequency, purpose and outcome of all contacts will be examined to estimate resource utilization.

## Clinical Investigation Plan

### **13. DATA COLLECTION, STUDY MONITORING, AND DATA DISCLOSURE**

#### **13.1. Data Collection and Reporting**

Electronic CRFs (eCRFs) will be utilized. Site staff will enter the information required by the protocol onto eCRFs using a validated sponsor system that conforms to IEC requirements for electronic data capture. All data fields will be completed where appropriate. However, if data are not available (i.e., missed visit, etc.), the site will receive instruction regarding electronic documentation. As data are entered, automated cross-check programs will search for any data discrepancies in the eCRFs. Appropriate error messages will be generated, allowing for the modification or verification of the entered data. Queries will generally be sent to the study site using an electronic data query system that includes an automated audit trail of the corrections.

Monitoring personnel of St. Jude Medical, or its designee, will review the eCRFs for completeness and accuracy and will instruct site personnel to make any corrections or additions. The Investigator, or designee, will certify that the data are complete and accurate by applying an electronic signature to the eCRF. Any subsequent alterations, corrections, or additions will be reviewed and electronically signed by the Investigator prior to database lock.

#### **13.2. Site Qualification**

A site visit will be performed by St. Jude Medical or designee prior to the start of the study to review the protocol in detail, to ensure the availability of appropriate trial personnel, adequate resources and to assess their ability to properly conduct the study according to ICH-GCP guidelines and local requirements.

#### **13.3. Training**

Detailed training to cover aspects of the hemodynamic management of heart failure (HF), identification of prospective patients, HF sensor implant procedures, the use of the heart failure electronic units, and the use of the Merlin.net website to view the patient's hemodynamic parameters will occur for all sites prior to enrollment of patients.

##### **13.3.1. Site Training**

All Investigators and clinical investigation personnel are required to attend Sponsor training sessions, which may be conducted at an Investigator's meeting, a site initiation visit or other appropriate training sessions. Over-the-phone or self-training may take place as required. Training of Investigators and clinical investigation personnel will include, but is not limited to, the CIP requirements, investigational device usage, electronic case report form completion, and clinical investigation personnel responsibilities. All Investigators and clinical investigation personnel that are trained must sign a training log (or an equivalent) upon completion of the training. Prior to signing the training log, Investigators and clinical investigation personnel must not perform any CIP-related activities that are not considered standard of care at the site. The CardioMEMS™ HF System physician training plan (document CL1002501) is designed to provide essential didactic and field training.

#### **13.4. Study Monitoring**

St. Jude Medical or designee will monitor the study to meet the sponsor's monitoring Standard Operating Procedures (SOPs), ICH-GCP guidelines, and applicable regulatory requirements and to ensure that study initiation, conduct, and closure are adequate.

*This confidential document is the property of Abbott and shall not be reproduced, distributed, disclosed or used without the express written consent of Abbott*

## Clinical Investigation Plan

Clinical Monitors will periodically audit CRFs/eCRFs and corresponding source medical records for each subject. The monitoring visits provide the Sponsor with the opportunity to evaluate the progress of the study, to verify the accuracy and completeness of CRFs/eCRFs, to resolve any inconsistencies in the study records, and to assure that all protocol requirements, applicable regulatory or country-specific regulations, other requirements, and Investigator's obligations are being fulfilled.

The Investigator and his/her staff will be expected to cooperate with St. Jude Medical personnel or agents of St. Jude Medical and to be available during the monitoring visits to answer questions sufficiently and to provide any missing information.

The Investigator(s)/institution(s) will permit direct access to source data/documents for trial-related monitoring, audits, IRB/IEC and regulatory inspection(s).

### **13.5. Source Data Verification**

Source data verification ensures accuracy and credibility of the data obtained. During monitoring visits reported data are reviewed with regard to being accurate, complete, and verifiable from source documents (e.g., subject files, physician notes, discharge summaries, operative records, etc.).

### **13.6. Definition of Source Data**

Source data includes all information in source documents (original records, certified copies of original records, and original data recorded on customized worksheets) and includes all original recordings or certified copies of clinical findings, observations, or other activities in a clinical trial necessary for the reconstruction and evaluation of the trial.

### **13.7. Data Disclosure and Subject Confidentiality**

Subject medical information obtained as a result of this study is considered confidential and disclosure to third parties other than those noted below is prohibited. All reports and communications relating to subjects in this study will identify each subject only by their number. Medical information resulting from a subject's participation in this study may be given to the subject's personal physician or to the appropriate medical personnel responsible for the subject's welfare. Data generated as a result of this study are to be available for inspection upon request by government regulatory agency auditors, the Sponsor and the IEC.

The information developed in this clinical study will be used by the Sponsor in the clinical development of the study device and therefore may be disclosed by the Sponsor as required for disclosure as to other clinical Investigators, to other companies, and to other government agencies.

## Clinical Investigation Plan

### **14. ETHICAL CONSIDERATIONS AND STUDY ADMINISTRATION**

#### **14.1. Human Subjects Protection**

Subject's informed consent has to be obtained and documented in accordance with local regulations, ICH-GCP requirements, and the ethical principles that have their origin in the principles of the Declaration of Helsinki.

Before initiation of this study, the Investigator or designee and the Sponsor will jointly develop the consent form. Written IEC approval of the protocol and the consent form must be provided to the Sponsor prior to enrollment of subjects. This approval must refer to the consent form and to the study title and protocol number as given by the Sponsor on the cover page of the protocol.

Prior to participation in the study, the written informed consent form must be signed and personally dated by the subject, and by the person who conducted the informed consent discussion (Investigator or designee). The subject must receive a copy of the signed and dated informed consent form. As part of the consent process, each subject must consent to direct access to his/her medical records for trial-related monitoring, auditing, IEC review, and regulatory inspection.

The informed consent form should be updated or amended whenever new information becomes available that may be relevant to the subject. The subject should then sign the revised informed consent form as directed by the IEC.

A list of IEC voting members, their titles or occupations, and their institutional affiliations should be provided to the Sponsor before study initiation.

The IEC must be notified of completion of the study and a final report must be provided to the IEC. A copy of these reports must be forwarded to the sponsor. The Investigator must maintain an accurate and complete record of all submissions made to the IEC, including a list of all reports and documents submitted. Adverse experiences which are reported to the regulatory agencies, as Expedited Safety Reports, must be submitted promptly to the IEC.

This trial will be conducted in accordance with ICH-GCP regulations.

#### **14.2. Protocol Amendments**

The Investigator will not modify the protocol without first obtaining concurrence in writing from the Sponsor. If an amendment is required, this must be made in written form and receive approval according to the appropriate SOP. All changes to the protocol must be submitted to the IEC. Protocol modifications that impact subject safety or the validity of the study must be approved by the IEC and submitted to the appropriate regulatory agencies before initiation.

#### **14.3. Retention of Records**

The Sponsor and Investigator/Site will archive and retain all documents pertaining to the clinical investigation as per the applicable regulatory record retention requirements. The Investigator must obtain permission from Sponsor in writing before destroying or transferring control of any clinical investigation records.

#### **14.4. Finance, Insurance, and Publication**

Insurance coverage will be handled according to local requirements.

Finance, insurance, and publication rights are addressed in separate agreements as appropriate.

*This confidential document is the property of Abbott and shall not be reproduced, distributed, disclosed or used without the express written consent of Abbott*

## Clinical Investigation Plan

### 16. APPENDIX A: Schedule of Events

	Screening	Baseline (Implant)	Month 1	Months 6 and every 6 Months thereafter until Study Termination
Procedures	Prior to Implant	(within 30 days of Screening)	Visit 1 (30 ± 7 days)	Visits 2-5 or Study Termination (± 30 day window)
Informed Consent	X			
Demographics	X			
Past Medical & Surgical History. Ejection Fraction is part of this assessment and must be obtained within 3 months of the baseline visit or prior to implantation.	X			
Inclusion/Exclusion Criteria Review	X	X		
GFR (within 2 weeks of the implant procedure)	X			
INR (if indicated)		X		
Pulmonary artery measurement		X		
Physical Examination (including weight)	X 	X 	X 	X 
NYHA HF Classification	X		X	X
Pulmonary Artery Angiography		X		
Sensor Implant		X		
Sensor Measurements		X	X (Investigator discretion)	X (Investigator discretion)
Adverse Events Assessment		X	X	X
HF Hospitalizations	X		X	X
Quality of Life Assessment (EQ-5D-5L)	X			X (6, 12, 18, 24 months)
Medication Assessment (heart failure)	X	X	X	X
Subject Contact Log 			X	X

 Includes weight, height and vital signs (temperature, blood pressure, pulse, respirations).

 Includes weight, vital signs and significant changes from previous physical examination

 To be completed each time contact is made between the site staff and a study subject

## Clinical Investigation Plan

### **17. APPENDIX B: NYHA Functional Classification for Heart Failure**

The New York Heart Association (NYHA) Functional Classification provides a simple way of classifying heart disease (originally cardiac failure), useful for pre-operative and post-operative assessment. It places subjects in one of four categories, based on how much they are limited during physical activity:

**Class I (Mild):** Subjects with no limitation of activities; they suffer no symptoms.

**Class II (Mild):** Subjects with slight, mild limitation of activities and suffer mild symptoms (slight swelling of extremities).

**Class III (Moderate):** Subjects with marked limitation of activity; they are comfortable only at rest.

**Class IV (Severe):** Subjects who are unable to do any physical activity without discomfort; they suffer with HF symptoms at rest and are confined to bed or chair.

## Clinical Investigation Plan

### **18. APPENDIX C: Management of Hemodynamic Parameters**

The CardioMEMS HF System allows intermittent assessment of pulmonary artery systolic, diastolic and mean pulmonary artery pressures. Hemodynamic information obtained by the system should be used for clinical decision making in addition to symptoms, weights or physical examination (traditional markers of volume).

#### Pulmonary Artery Pressure Ranges:

PA Systolic	15 - 35 mmHg
PA Diastolic	8 - 20 mmHg
PA Mean	10 - 25 mmHg

Initially, thresholds will be set automatically at the acceptable range. The physician can adjust the thresholds specifically for each patient. These threshold notifications are intended to guide the physician to review the Merlin.net website. Every attempt should be made to keep the pulmonary artery pressures within the specified pulmonary artery pressure ranges utilizing the guidelines. In order to clinically manage patient's PA pressures, the physician must review the PA pressure measurements on a frequent basis, for example, some patients may require a daily review of their PA pressure measurements, while some patients may need a weekly review. The physician or designee has unlimited access to the Merlin.net website.

An elevation of pressures beyond the patient's pressure ranges should be considered a volume overloaded status and should be managed according to the hyper-volemic guidelines (see below). Diuretics and vasodilators should be adjusted based on the patient's baseline diuretic requirement, knowledge of the patient's prior response to these agents, and clinician judgment to accomplish the pressure goals set forth in this guideline.

A decrease in the pulmonary pressures below the patient's pressure ranges should be considered a volume depletion event and managed according to the hypo-volemia guidelines (see below) (see below). Diuretic therapy should be held and the chronic dose should be lowered.

In addition to these specific guidelines, the physician should also incorporate the recommendations set forth in the ACC/AHA 2013 Guidelines for the Diagnosis and Management of Heart Failure in the Adult or in the ESC Guidelines on Acute and Chronic Heart Failure 2016.

The PA pressure readings should be used in addition to weights, signs and symptoms, laboratory values and other traditional markers of volume in the management of heart failure. It is important to review the trend of PA pressures. As with all other diagnostic information, physicians should consider the entire medical history of each patient when initiating or modifying therapies.

#### Elevated PA Pressures (Hyper-volemic)

##### Hyper-volemic Definitions

- Subject symptoms: Congestive symptoms (wet)

*This confidential document is the property of Abbott and shall not be reproduced, distributed, disclosed or used without the express written consent of Abbott*

## Clinical Investigation Plan

- CardioMEMS HF System Parameters: above the acceptable range
- Daily trends: elevated trend data outside the acceptable range
- Weekly trends: elevation in trend data

### Treatment Recommendations

- Add or increase diuretic (and appropriate electrolyte replacement)
  - a. Increase or add loop diuretic
  - b. Change to another loop diuretic
  - c. Add thiazide diuretic (with caution)
  - d. IV doses of loop diuretic
  - e. Serum electrolyte evaluation with change in baseline medication
  - f. Re-assess pulmonary artery pressure utilizing the CardioMEMS HF System at least 2 – 3 days per week until optimolemic
- Add or increase vasodilators including long-acting nitrates
- Re-educate in salt intake and fluid restriction
- If subject has signs and symptoms of poor perfusion (cold) in addition to being hyper-volemic:
  - a. Consider admission if clinical evidence suggests need for IV diuretics, telemetry monitoring or the IV therapeutic agents
  - b. Consider invasive hemodynamic monitoring for determination of Cardiac Output, if indicated

### Low PA Pressures (Hypo-volemic)

#### Hypo-volemic Definitions

- Subject symptoms: poor perfusion in absence of signs and symptoms of congestion
- CardioMEMS HF System Parameters: below the acceptable range
- Daily trends: decrease in trend data outside the acceptable range
- Weekly trends: decrease in trend data

### Treatment Recommendations

- Lower or discontinue diuretic
  - a. If on a thiazide diuretic with loop diuretic, lower or discontinue the dose of thiazide (and adjust electrolyte replacement)
  - b. If on only loop diuretic, lower the dose or discontinue
  - c. Consider liberalization of oral fluid restriction and salt restriction
- If postural hypotension, hold or lower vasodilators and/or oral nitrates, especially if hypotensive when sitting or supine

*This confidential document is the property of Abbott and shall not be reproduced, distributed, disclosed or used without the express written consent of Abbott*

## Clinical Investigation Plan

- If worsening renal function, hold or lower ACE/ARB dose, especially if hypotensive
- If subject had signs and symptoms of poor perfusion (cold) in addition to being hypovolemic:
  - a. Consider admission if clinical evidence suggests need for IV fluid repletion, telemetry monitoring or the use of IV therapeutic agents
  - b. Consider invasive hemodynamic monitoring for determination of Cardiac Output, if indicated

### Recommended Frequency of CardioMEMS HF System Review

Subject Status	Weekly	At least 2–3 times per week until optivolemic	At least 2–3 times per week until pressure stabilizes
Acceptable PA Pressure (Opti-volemic)	X		
Elevated PA Pressure (Hyper-volemic)		X	
Low PA Pressure (Hypo-volemic)		X	
Medication modifications			X
Significant deviations in trend data			X

*This confidential document is the property of Abbott and shall not be reproduced, distributed, disclosed or used without the express written consent of Abbott*

## Clinical Investigation Plan

### **19. APPENDIX D: BMI Calculator**

To calculate subjects Body Mass Index using the website below:

<http://www.nhlbisupport.com/bmi/bmi-m.htm>

Enter the subjects Weight and Height and then calculate BMI (print screen for source documentation)

Formulas used to calculate Body Mass Index:

English BMI Formula

BMI = Weight in pounds/ (height in inches x height in inches) x 703

Metric BMI Formula

BMI = Weight in kilograms/ (height in meters x height in meters)

Note that BMI may also be calculated within the eCRF.

### **20. APPENDIX E: Glomerular Filtration Rate**

To calculate subjects Glomerular Filtration Rate use the website below:

<http://www.nephron.com/cgi-bin/CGSI.cgi>

Enter the subjects Creatinine level, Age, Race, Gender then calculate (print screen for source documentation)

GFR (mL/min/1.73 m^2) = 186 x(Scr)-1.154 x (Age)-0.203 x (0.742 if female) x (1.210 if African American)

Note that GFR may also be calculated within the eCRF.

## Clinical Investigation Plan

### **21. APPENDIX F: Protocol Definitions**

**Enrollment** – After signing the Informed consent, meeting study inclusion criteria and following successful Sensor implant, subjects are considered enrolled.

**HF Hospitalization** – A HF hospitalization of greater than or equal to 24 hours in a hospital

**Active Infection**- Febrile, elevated WBC, left shift, on antibiotics, positive cultures (blood, sputum or urine).

**PI** – Appropriate clinician designated as the Principal Investigator on the “Investigator Agreement” received and approved by St. Jude Medical. For study related procedures/visits PI refers to the PI or his/her designee.

**Source documents** – Primary study documentation including electronic, paper, phone messages, etc. containing study-pertinent information such as visit information, clinical history, medications, (S)AE reporting, etc. These documents are originals and should be treated as such. Information from these documents will be transferred from and compared against information reported in study CRFs.

**Sub-investigator** – Clinical personnel designated as a sub-investigator on the “Investigator Agreement” received and approved by St. Jude Medical.

**Worksheets** –Source documents used for calculation of clinical values such as BMI or EGFR from screening to end of study. Worksheets may also be used during the sensor implant or follow-up visits to capture information not captured in the medical record. In order for these worksheets to be considered valid, the Investigator must sign and date the worksheet.

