## Clinical Investigation Plan

Number of Subjects	Up to 800 subjects will be enrolled. Enrollment will be limited to 15% of the total study population at any one site.
Number of Sites:	This is a prospective, multi-center, open-label clinical trial to be conducted at up to 85 sites.
Safety Measures:	
Primary safety endpoints will be evaluated at 2 years: 1) freedom from device/system related complications and 2) freedom from pressure sensor failure.
 
Safety will also be assessed throughout the study by the frequency of Adverse Device Effects (ADEs), Serious Adverse Events (SAEs), and Serious Adverse Device Effects (SADEs).

Effectiveness Measures:	
The primary effectiveness endpoint is the annualized HF hospitalization rate at 1 year.
 
Supplemental analyses include mortality at 1 year, HF hospitalization or death at 1 year, patient compliance over the trial, training evaluation, and subgroup analyses.
 
Information regarding all hospitalization and deaths will be collected throughout the study.

Statistical Considerations:	
Primary Safety Endpoints            The primary safety hypotheses are that the device / system-related complication-free proportion of subjects will be at least 80% at 24 months (OPC used in the CHAMPION trial) and that the pressure sensor failure-free proportion of subjects will be at least 90% at 24 months (OPC used in the CHAMPION trial). Plotting and analysis of safety endpoints will also be displayed using Kaplan-Meier methods.            All safety analyses will be performed on the safety population.
 
Primary Effectiveness Endpoint            The primary effectiveness evaluation will compare the annualized HF hospitalization rate at 1 year compared to the HF hospitalization rate in the year prior to enrollment.            The effectiveness population consists of all subjects who received a sensor implant regardless of study completion status.
 
Supplemental Analyses            Mortality at 1 year will be analyzed. Plotting and analysis of mortality will be displayed using Kaplan-Meier methods.            The annualized HF hospitalization or death rate at 1 year in study will be compared to the HF hospitalization rate in the year prior to enrollment.

*This confidential document is the property of Abbott and shall not be reproduced, distributed, disclosed or used without the express written consent of Abbott*

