- Follow-up study visits will be scheduled at Month 1, Month 6, and every 6 months thereafter for 2 years. Follow-up visits will include a physical exam, evaluation of NYHA Class (Appendix B), AE assessment, heart failure medications review, quality of life assessment, and assessment of any hospitalizations (including HF hospitalizations), that may have occurred between visits.

In addition, all contacts between site staff and study subjects post implant will be recorded on a log to capture frequency, purpose and outcome of each contact.

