#### **6.1. Inclusion Criteria**

1. Written informed consent obtained from subject
2.  $\geq 18$  years of age
3. Diagnosis of NYHA Class III Heart Failure
4. At least 1 HF hospitalization within 12 months of Baseline visit
5. Subjects with reduced LVEF heart failure should be receiving a beta blocker for 3 months and an ACE-I or ARB for one month unless in the investigator's opinion, the subject is intolerant to beta blockers, ACE-I or ARB.
6. Subjects with a BMI  $\leq 35$ . Subjects with BMI  $>35$  will require their chest circumference to be measured at the axillary level, if  $> 65$  inches the patient will not be eligible for the study.
7. Subjects with pulmonary artery branch diameter  $\geq 7\text{mm}$  - (implant target artery - assessed during the RHC)
8. Subjects willing and able to comply with the follow-up requirements of the study

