#### **8.1. Screening Visit**

During the screening visit, the following procedures/assessments will be performed to determine subject eligibility:

- Informed Consent prior to the conduct of any study-related procedures
- Physical examination including vital signs (temperature, heart rate, blood pressure), weight, height, BMI calculation (refer to Appendix D)
- Medical and surgical history including ejection fraction data must be taken within the last 3 months to enroll in the study. If ejection fraction data is older than six months, ejection fraction data is required to be obtained at screening visit or prior to implantation.
- Patient history of all heart failure hospitalizations in the 12 months previous to the baseline visit as documented with information provided by the patient's cardiologist, internist, or referring physicians and review of all source documents of any heart failure hospitalizations reported in the previous year.
- Demographics
- NYHA Functional Classification
- Calculation of GFR (requires creatinine - refer to Appendix E)
- Assessment of medications
- Assessment of enrollment eligibility (inclusion/exclusion criteria)
- Completion of Quality of Life Questionnaire EQ-5D-5L

Eligible subjects will be scheduled for the Implant procedure. Subjects on anticoagulation therapy (e.g. warfarin) may be instructed by the Investigator to discontinue use 1-2 days prior to pressure sensor placement. The investigator should consider utilizing enoxaparin (Lovenox) per the site's standard of care as bridge therapy to Sensor placement in subjects who were on anticoagulation therapy.

For subjects at risk for gastro-intestinal bleeding during the period in which dual antiplatelet therapy is given, the investigator should consider a proton pump inhibitor such as omeprazole (Prilosec). Subjects at risk include the elderly, those with a history of gastroduodenal ulcers, GERD, esophagitis, intestinal polyps or cancer. Subjects who smoke or who are using steroids or non-steroidal anti-inflammatory drugs may also be at risk.

*This confidential document is the property of Abbott and shall not be reproduced, distributed, disclosed or used without the express written consent of Abbott*

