## Clinical Investigation Plan

Implanted subjects will be evaluated at Month 1 ( $\pm$  7 days) and at Months 6, 12, 18, and 24 ( $\pm$  30 days) and the following procedures/assessments will be performed:

- Updated medical and surgical history
- Assessment of SAEs, ADEs, and SADEs that occurred since the last visit
- Reporting of any HF hospitalizations that have occurred since the last visit
- Abbreviated physical examination (significant changes since previous visit) including vital signs (heart rate, blood pressure), and weight
- Assessment of NYHA functional class
- Completion of Quality of Life Questionnaire EQ-5D-5L (6, 12, 18, and 24 month visits)
- Heart failure medication review
- PA pressure measurements may be obtained at the Investigator's discretion

Subjects will be reminded to obtain pulmonary artery pressure measurements utilizing the CardioMEMS HF System as directed. Subjects will be reminded of the current ACC/AHA guidelines or of the ESC guidelines regarding sodium and fluid restrictions.

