#### **11.2. Serious Adverse Event (SAE)**

If the AE meets any of the criteria below, it is regarded as a serious adverse event (SAE).

- a) Led to a death,
- b) Led to a serious deterioration in health of the subject, that either resulted in
  - 1. a life-threatening illness or injury, or
  - 2. a permanent impairment of a body structure or a body function, or
  - 3. in-patient hospitalization or prolongation of existing hospitalization, or
  - 4. medical or surgical intervention to prevent life threatening illness or injury or permanent impairment to a body structure or a body function.
  - 5. chronic disease
- c) Led to fetal distress, fetal death or a congenital abnormality or birth defect.

**Note:** A planned hospitalization for pre-existing condition, or a procedure required by the CIP, without a serious deterioration in health, is not considered to be an SAE.

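### HF hospitalization has a 24-hour floor but no criterion for heart failure as the cause, and the two years that the primary test compares are ascertained by different procedures

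*Combined protocol and SAP*

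**What the plan says.** **Definition.** Appendix F holds the only definition of the event: "A HF hospitalization of greater than or equal to 24 hours in a hospital". Sections 10.1 and 12.8.1, which state the endpoint and the test, add no criterion for cause.

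**Prior year.** Section 8.1 asks at screening for "Patient history of all heart failure hospitalizations in the 12 months previous to the baseline visit", using information from the cardiologist, internist or referring physicians, together with "review of all source documents of any heart failure hospitalizations reported in the previous year". Inclusion criterion 4 in section 6.1 requires "At least 1 HF hospitalization within 12 months of Baseline visit".

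**Study year.** Section 8.3 asks at each follow-up visit for "Reporting of any HF hospitalizations that have occurred since the last visit". Section 5 widens this to "assessment of any hospitalizations (including HF hospitalizations), that may have occurred between visits", and the synopsis states: "Information regarding all hospitalization and deaths will be collected throughout the study". Section 11.2 also lists "in-patient hospitalization or prolongation of existing hospitalization" among the SAE criteria, with no minimum stay, and section 11.5 sets a 3-calendar-day reporting limit.

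**Who classifies.** The trial is open-label, and section 5 has the investigator or designee review PA pressures at least weekly. No current section describes adjudication, and the Appendix G entry for version B records that there is no events committee.

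**Test.** Section 12.8.1 compares the 12-month rate with the prior-year rate by a one-sample, one-sided Poisson test. Success requires the upper 97.5% confidence limit to lie below the prior-year rate.

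**The concern.** The definition uses the term it is meant to define. It does not say whether heart failure must be the primary reason for the stay or may be contributory, or which signs, symptoms or treatment establish it. With up to 85 sites, that gap is filled locally, event by event, and an analyst cannot repair it afterwards.

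This would matter less if both years were counted in the same way. They are not. Before implant, only admissions already labelled HF are sought and reviewed. After implant, all hospitalizations are collected and the HF subset is picked out by staff who manage the patient and can see the pressures. There is no control arm in which the difference would cancel, so it becomes part of the apparent effect. The supplemental comparison of HF hospitalization or death (section 12.8.2.2) and the effectiveness subgroups (section 12.8.2.5) use the same event.

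**Working it through.** **1. Reproduce the plan's figure.** Inputs from section 12.2: λ0 = 1.00, λ1 = 0.75, one-sided alpha 0.025. The exact rule takes the largest count c with P(X ≤ c | nλ0) ≤ 0.025; power is P(X ≤ c | nλ1), X being Poisson. For n = 149, c = 125, actual alpha is 0.0247 and power is 0.9016. These match the table, as do its other five rows. No sample size figure is in dispute.

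**2. Find the success boundary.** Section 12.2 names 250 subjects for effectiveness and a planned enrolment of 800 (up to 800 in the synopsis). With a prior-year rate of 1.0:

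- n = 250: c = 218; 218/250 = 0.872
- n = 800: c = 744; 744/800 = 0.930

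At 800 subjects, an observed rate 7% below the recorded prior-year rate is enough (1 − 0.930 = 0.070).

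**3. Add a counting difference.** Let s be in-study capture relative to prior-year capture. Assumptions: no true change, recorded prior-year rate 1.0 taken as fixed (as the plan does), one full year of follow-up for everyone. The chance of success is P(X ≤ c | n × 1.0 × s). The documents give no capture or misclassification rate, so s is an assumption, shown in both directions.

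| s | n = 250 (c = 218) | n = 800 (c = 744) |
|---|---|---|
| 1.05 | 0.3% | below 0.1% |
| 1.00 | 2.1% | 2.4% |
| 0.95 | 11% | 29% |
| 0.90 | 34% | 82% |

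For example, at n = 800 and s = 0.90 the expected count is 720 and P(X ≤ 744 | 720) = 0.820. At s = 1.05 it is 840 and P(X ≤ 744 | 840) is about 0.0004.

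These figures isolate counting. They leave out regression to the mean and sampling error in the prior-year rate.

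**4. Ask which way s is likely to fall.** The text points both ways:

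- *Towards s below 1:* an HF label on a borderline prior-year stay can qualify a subject for entry; in-study events are classified open-label by the managing site; the 24-hour floor might in practice be checked more strictly in study.
- *Towards s above 1:* in-study capture is broader (all hospitalizations, plus SAEs) and prospective; prior-year admissions not labelled HF are never looked at; and Appendix C treats pressures above range as volume overload, so seeing them may push a site towards the HF label.

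Nothing in the documents allows these to be netted off.

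**The case against.** Four points can fairly be made for the plan.

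- **One definition, both years.** A reader might infer that the 24-hour floor applies only in study, or that two definitions conflict. The text does not support that. Appendix F has no period restriction, and the same term runs through sections 6.1, 8.1, 8.3 and 12.8.1. What is missing is an explicit check of stay length and cause for prior-year events. The eCRF pages are not in the documents, so admission and discharge dates may already be collected.
- **Source review.** Section 8.1 requires review of source documents for reported prior-year events, and sections 13.4 and 13.5 add monitoring and source verification. This narrows the difference between the years. It cannot test a cause criterion that was never written, and it does not reach prior-year stays that nobody reported as HF.
- **Direction.** A reader might infer that the difference favours the device. It can, but broader in-study capture can work against it, as step 4 of the working shows.
- **Illustrative rates.** The capture ratios are assumed. The 82% is one cell of a range and not an estimate of this trial's false-positive rate.

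All four stand as limits. None supplies a criterion for heart failure as the cause, or a common procedure for the two years.

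**Conclusion.** The point holds in this form: the primary event lacks a cause criterion, the two years are ascertained by different procedures, no adjudication is described, and the test passes any net counting difference straight into the result. The sign of that difference is unknown.

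The test is sensitive to it. Under the assumptions in the working, a net shortfall of about 7% in study reaches the success boundary at 800 subjects, and about 13% does so at 250 (1 − 0.872 = 0.128). A net excess lowers the chance of success and could hide a real benefit. The change should be made; the sample size needs no revision on this account.

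**What to change.** - **Definition.** Keep the floor of at least 24 hours. Replace the Appendix F entry with one operational endpoint definition: worsening heart failure, documented in source records as the primary reason for the stay, by stated signs or symptoms and by HF-directed treatment during the stay.
- **Same net in both years.** List all hospitalizations in the 12 months before baseline, as is already done in study.
- **Same form.** For every hospitalization in either year, record admission and discharge dates and each criterion on the same eCRF page, from source.
- **Counting rule.** Count only events that meet the definition, in both years. Keep a subject in the effectiveness population if the qualifying event turns out not to meet it.
- **Sensitivity analysis.** Repeat the primary comparison with events as reported by the sites.

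The cost is definition text, one common eCRF page and some extra site data entry; section 8.1 already requires source review for reported prior-year events. Some events will drop out on either side, possibly more in the prior year where records are thin, which is why the analysis of events as reported is needed. Sites would still complete the form open-label, so the change reduces the difference between the years without removing site judgement.
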